2. The patient has been diagnosed with a complex regional pain syndrome, failed back surgery syndrome, persistent or prevalent pain symptoms related to systemic disease (e.g., diabetic peripheral neuropathy, post-herpetic neuropathy), untreated hyperparathyroidism, or a history of prior surgery, trauma or other source of pain that, in the Investigator's opinion, would confound or interfere with the assessment of the patient's fibromyalgia pain or require excluded therapies during the patient's study participation.
3. The patient has any lifetime history of bipolar disorder, schizophrenia, schizoaffective disorder, or other psychotic disorder as determined at Screening either by history or by the Mini International Neuropsychiatric Interview, Version 7.0.2 (MINI 7.0.2) Module A (Major Depressive Episode), Module C (Manic and Hypomanic Episodes), and Module K (Psychotic Disorders).
4. History of or evidence for a diagnosis of borderline personality disorder (BPD) based on a score of ≥ 7 on the McLean Screening Instrument for BPD (MSI-BPD) at Visit 1 (Screening). Any patient who scores ≥ 7 on the MSI-BPD may be randomized only with Medical Monitor approval.
5. The patient is at increased risk of suicide on the basis of the Investigator's judgment, or the results of the Beck Depression Inventory-II (BDI-II) (a response > 1 to BDI-II item #9), or the results of the Columbia Suicide Severity Rating Scale (C-SSRS) conducted at Screening and Baseline (e.g., C-SSRS Type 3, 4 or 5 ideation during the preceding 6 months and any suicidal behavior within the past 12 months).
6. A BDI-II score greater than 24 at either the Screening or Baseline visit.
7. The patient has participated in any other study with TNX-102 SL.
8. Based on screening laboratory results, TSH > 1.5 times the upper limit of normal or AST or ALT > 2 times the upper limit of normal; or, in the Investigator's opinion, evidence of a clinically significant laboratory abnormality based on Screening laboratory tests or medical history.
9. Diagnosed with clinically significant and currently relevant cardiac disease (e.g., significant arrhythmia; heart block; heart failure; symptomatic coronary artery disease), recent myocardial infarction [within the past 2 years] or QTcF > 450 msec (male) or > 470 msec (female) on the screening electrocardiogram (ECG).
10. The patient has a known current clinically significant systemic infection (e.g., HIV, hepatitis).

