8.3. Patient Exclusion Criteria

Eligible patients who meet any of the following criteria during the screening period should be excluded from the study:

1. The patient has been diagnosed with infectious or inflammatory arthritis (e.g., rheumatoid arthritis, ankylosing spondylitis, psoriatic arthritis), systemic lupus erythematosus, untreated or active gout, (i.e. any acute attack within past 2 years is exclusionary), or meets criteria for other type of systemic autoimmune disease.
2. The patient has been diagnosed with a complex regional pain syndrome, failed back surgery syndrome, persistent or prevalent pain symptoms related to systemic disease (e.g., diabetic peripheral neuropathy, post-herpetic neuropathy), untreated hyperparathyroidism, or a history of prior surgery, trauma or other source of pain that, in the Investigator's opinion, would confound or interfere with the assessment of the patient's fibromyalgia pain or require excluded therapies during the patient's study participation.
3. The patient has any lifetime history of bipolar disorder, schizophrenia, schizoaffective disorder, or other psychotic disorder as determined at Screening either by history or by the Mini International Neuropsychiatric Interview, Version 7.0.2 (MINI 7.0.2) Module A (Major Depressive Episode), Module C (Manic and Hypomanic Episodes) and Module K (Psychotic Disorders).
4. History of or evidence for a diagnosis of borderline personality disorder (BPD) based on a score of ≥ 7 on the McLean Screening Instrument for BPD (MSI-BPD) at Visit 1 (Screening). Any patient who scores ≥ 7 on the MSI-BPD may be randomized only with Medical Monitor approval.
5. The patient is at increased risk of suicide on the basis of the Investigator's judgment, or the results of the BDI-II (a response > 1 to BDI-II item #9), or the results of the C-SSRS conducted at Screening (e.g., any C-SSRS Type 3, 4 or 5 suicidal ideation during the preceding 6 months and any suicidal behavior within the past 12 months) and Baseline (e.g., any C-SSRS Type 3, 4, or 5 suicidal ideation or any suicidal behavior since Screening visit).
6. A BDI-II score greater than 24 at either the Screening or Baseline visit.
7. The patient has participated in any other study with TNX-102 SL.

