8. Based on screening laboratory results, thyroid-stimulating hormone (TSH) > 1.5 times the upper limit of normal or aspartate aminotransferase (AST) or alanine aminotransferase (ALT) > 2 times the upper limit of normal; or, in the Investigator's opinion, evidence of a clinically significant laboratory abnormality based on Screening laboratory tests or medical history.
9. Diagnosed with clinically significant and currently relevant cardiac disease (e.g., significant arrhythmia; heart block; heart failure; symptomatic coronary artery disease), recent myocardial infarction [within the past 2 years]) or QTcF > 450 msec (male) or > 470 msec (female) on the screening electrocardiogram (ECG).
10. The patient has a known current clinically significant systemic infection (e.g., HIV, hepatitis).
11. The patient is currently receiving or is expected to need systemic corticosteroids (>5 mg prednisone or equivalent per day) or has received acute treatment with systemic or locally injected corticosteroids within 28 days of the Baseline visit, or is likely to require such treatment during the study.
12. The patient has received tender point, trigger point or other local injections with anesthetic agents (or corticosteroids, as per EC#11) within 28 days of the Baseline visit, or is unable to refrain from such injections during the study.
13. The patient is unable to successfully wash-out of the following medications during screening, or wash-out is inadvisable: monoamine oxidase inhibitors (30 days), levomilnacipran, anticonvulsants (except when used for migraine prophylaxis), amphetamine mixed salts, weight loss agents such as phentermine and diethylpropion, muscle relaxants (e.g., methocarbamol, baclofen, carisoprodol), stimulants (e.g., methylphenidate, lisdexamfetamine, dextroamphetamine), mirtazapine, trazodone, nefazodone, St. John's wort, any medication known to be a strong CYP3A4 inhibitor ([Appendix 1](#)), or any of the medications listed in Inclusion Criterion #6.

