before randomization may occur. Therefore, these patients will need to return for an unscheduled visit after the first 2 weeks of washout have been completed. All benzodiazepine drug screening must be sent to the central laboratory for analysis, hence results may be delayed; all other repeat urine drug screening may be conducted on-site. Patients do not have to wait for confirmation of negative centralized benzodiazepine results before starting their 7-day baseline data collection phase, but all results must be confirmed negative prior to randomization.

Patients with a positive screening UDS due to an allowed prescription drug (e.g., headache remedies containing butalbital) do not require further drug screening.

Each clinically significant abnormal laboratory value or other clinically meaningful abnormality should be followed until the abnormality resolves or until a decision is made that it is not likely to resolve. If such abnormalities do not return to normal within a reasonable period, their etiology should be identified and Tonix or designee should be notified. Clinically significant abnormalities in laboratory values after the Screening visit labs will be recorded as AEs.

NOTE: A screening TSH level greater than 1.5 times higher than the upper limit of normal, or ALT or AST level > 2 times the upper limit of normal, is exclusionary; however, the patient may remain in screening to undergo repeat LFT assessments if a transient abnormality (eg, viral illness; effects of a medication being discontinued, etc) is thought to be responsible for their initial elevation.

Table 3: Clinical Laboratory Assessments

Clinical chemistry	Hematology
Alanine aminotransferase (ALT/SGPT) ^a	Hematocrit
Alkaline phosphatase	Hemoglobin
Aspartate aminotransferase (AST/SGOT) ^a	MCH concentration (MCHC)
Bicarbonate	Mean corpuscular hemoglobin (MCH)
Bilirubin (direct and total)	Mean corpuscular volume (MCV)
Blood urea nitrogen (BUN)	Platelet count
Calcium	Red blood cell (RBC) count
Chloride	WBC differential
Cholesterol (total)	Neutrophil count (absolute and %)
Creatine kinase (CK)	Lymphocyte count (absolute and %)
Creatinine	Monocyte count (absolute and %)
Glucose	Eosinophil count (absolute and %)
LDH	Basophil count (absolute and %)
Phosphorus	White blood cell (WBC) count
Potassium	Red blood cell distribution width (RDW)
Protein (albumin and total)	
Sodium	
HbA1c only if glucose > 180 mg/dL	

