Thyroid-stimulating hormone (TSH) ^c at screening	Serum Pregnancy Test at Screening ^b
Free T4 only if TSH is outside of normal limits	Urine Pregnancy Test (qualitative dipstick) ^b
Pharmacogenomic testing (optional; can be obtained at any visit post-Screening, including an Early Termination visit)	Urine Drug Screen ^d

^a Level greater than 2 times the upper limit of normal is an exclusion (if persistent upon repeat).

- ^b Pregnancy testing for females of child-bearing potential only. A positive pregnancy test is exclusionary (Visit 1 or Visit 2) or mandates withdrawal from the study (all other visits).
- ^c TSH level greater than 1.5 times higher than the upper limit of normal is exclusionary at Visit 1.
- ^d Urine drug screening will be conducted on all patients at Screening and, if necessary, prior to the beginning of the 7-day baseline data collection phase in patients washing off opioids, amphetamines, or benzodiazepines and who otherwise qualify for the study.

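### Exclusion criterion 8 fixes a TSH limit only on the high side and no criterion names hyperthyroidism, which the reference drug's label contraindicates: a cheap safety improvement

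*Protocol*

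**What the plan says.** Protocol 8.3 opens its list with "Eligible patients who meet any of the following criteria during the screening period should be excluded from the study". Criterion 8 then gives two routes to exclusion. The first is numeric and covers TSH and the transaminases; for TSH it is "thyroid-stimulating hormone (TSH) > 1.5 times the upper limit of normal". The second depends on the investigator's opinion that there is "evidence of a clinically significant laboratory abnormality based on Screening laboratory tests or medical history".

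The TSH limit is repeated in the synopsis ("TSH > 1.5 times the upper limit of normal or AST or ALT > 2 times the upper limit of normal"), in the note in 12.3.7 ("A screening TSH level greater than 1.5 times higher than the upper limit of normal") and in footnote c to Table 3 ("TSH level greater than 1.5 times higher than the upper limit of normal is exclusionary at Visit 1"). Table 3 also provides a reflex test: "Free T4 only if TSH is outside of normal limits". Table 2, footnote d, confines TSH testing to Screening.

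Three other provisions can reach a thyroid problem without naming it: exclusion criterion 19 (significant, uncontrolled or unstable medical conditions), inclusion criterion 9 (Medical Monitor approval before randomization, for every patient), and randomization criterion 1 in 8.4 (a re-check of all criteria, with blood results).

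Section 5.2 names the extended-release cyclobenzaprine capsule as the reference listed drug. Its label, in Appendix 2, lists hyperthyroidism as a contraindication in the highlights, in label section 4 and in the patient information.

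**The concern.** A rule that excludes only high TSH points toward an underactive thyroid. The usual laboratory picture of hyperthyroidism is the reverse, a suppressed TSH with raised free T4, and an upper TSH limit cannot detect it. So the thyroid condition that the appended label contraindicates is the one for which the protocol states no fixed rule, although the tests that would show it are already planned.

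What is at stake is patient safety, to a small degree. With 35 to 45 sites, a written rule gives a consistency that separate opinions do not. Later detection is limited: TSH and the ECG are scheduled at Screening only, and vital signs are not required at telephone visits (Table 2, footnotes d, f and g). Nothing in the efficacy analysis depends on this.

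**Working it through.** No calculation applies, and the plan states no figure to reproduce. The check sets the eligibility text beside the label.

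**1. Direction of the numeric TSH rule.**

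| Place in the protocol | Upper limit | Lower limit |
|---|---|---|
| Synopsis, exclusion 8 | 1.5 × ULN | none |
| 8.3, exclusion 8 | 1.5 × ULN | none |
| 12.3.7, note | 1.5 × ULN | none |
| Table 3, footnote c | 1.5 × ULN | none |

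Four of four statements set an upper limit and none sets a lower one. No eligibility limit is given for free T4.

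**2. Is the condition named elsewhere?** Exclusion criteria 1 to 29, the inclusion criteria and the randomization criteria do not name hyperthyroidism. Criterion 2 names hyperparathyroidism, which is a different disorder. The count is 0 of 29 exclusions.

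**3. The label's contraindications against the exclusions.**

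| Label section 4 | Named in 8.3? | How |
|---|---|---|
| Hypersensitivity | yes | Criterion 22 |
| MAO inhibitors (with the drug or within 14 days) | yes | Criterion 13, with a 30-day washout |
| Recovery from myocardial infarction, arrhythmia, conduction disorder, heart failure | yes, filtered | Criterion 9: "Diagnosed with clinically significant and currently relevant cardiac disease", plus fixed limits for recent infarction and QTcF |
| Hyperthyroidism | no | – |

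Three of four groups are named, one of them through a clinical-significance filter. One is not named.

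**4. What happens to a patient with a low TSH at Screening?** The result is outside normal limits, so free T4 is run. If the investigator judges the abnormality clinically significant, three things follow. It is recorded in medical history (12.3.1). It is followed until it resolves or is judged unlikely to; if it has not normalised within a reasonable period, its cause is to be identified and the sponsor or its designee notified (12.3.7). The patient is also excluded under the second part of criterion 8. Criterion 19 and inclusion criterion 9 offer two further stops.

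That makes three routes to exclusion, each resting on judgement. A high TSH above the limit excludes without any opinion being formed; a low TSH with a high free T4 does not.

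**5. Affected patients.** The documents give no thyroid prevalence or screening data, so no number of affected patients can be derived and none is claimed.

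**The case against.** The strongest reply is that the condition is already covered. The second part of criterion 8 reaches both a known diagnosis and a low TSH with high free T4. Once the investigator forms that opinion, exclusion follows under the same opening sentence as the numeric limit. The criteria are re-checked at Baseline, and the Medical Monitor approves every patient. This stands, and it is why the gain is small. A reader might infer that a low TSH leads to nothing, or that hyperthyroid patients would be enrolled freely. The documents support neither reading: free T4 and follow-up are prescribed, and there are three routes to exclusion.

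A second reply is that the label is not the trial's eligibility standard. It covers 15 to 30 mg orally for up to 2 or 3 weeks; the study gives 2.8 to 5.6 mg sublingually for 14 weeks. Nothing says that the TSH rule was written to implement the label, so it should not be called a failed attempt to do so. This also stands. However, the lower dose did not stop the sponsor from naming exclusions for the other three contraindication groups, the treatment period is longer than the labelled one, and 14.4 itself refers to this label on pregnancy.

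A third reply is that judgement is used for other contraindications too: criterion 9 is filtered by significance, and criterion 13 depends partly on whether washout is advisable. That is true, but both name the condition or drug, and hyperthyroidism is not named at all.

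Finally, a reason may exist out of sight. Section 5.3.2 shows no text, 5.3.3 and 5.4 are partly redacted, and 16.1 refers investigators to an Investigator's Brochure that is not available here. This cannot be ruled out.

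**Conclusion.** The point holds as a cheap improvement to one eligibility rule. All four statements of the TSH limit look only upward, no criterion names hyperthyroidism, and it is the only one of the label's four contraindication groups without a named exclusion. Free T4 testing and follow-up of abnormal values exist, but neither carries a mandatory eligibility consequence, so exclusion depends on investigator opinion and Medical Monitor approval.

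The size is small: overt disease is unlikely to get past those reviews. The conclusion does not extend to an absence of safeguards. It also does not extend to a low TSH alone or to treated patients who are now euthyroid, since neither is clearly the contraindicated condition.

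It rests on two assumptions: that the reference label is a relevant safety source for the same active ingredient at a lower sublingual dose, and that no reason for the omission lies in text not shown or in the Investigator's Brochure. Endpoint, alpha and power are not affected.

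**What to change.** Add to exclusion criterion 8, in the synopsis and in 8.3: *Current hyperthyroidism, defined as a known active diagnosis or a Screening TSH below the lower limit of normal with free T4 above the upper limit of normal.* Align the note in 12.3.7 and Table 3 (footnote c and the free T4 row). Leave low TSH with normal free T4, and treated euthyroid patients, to the existing Medical Monitor review. If the sponsor has a reason not to apply this contraindication at the study dose, stating it in the protocol would serve instead.

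The cost is one sentence carried into four places, in an amendment that needs ethics committee or IRB approval (15.1) while the trial is under way, and a few extra screen failures. No new test is needed. Waiting for free T4 should add little time, because 11.1.2 already recommends at least 10 days between Screening and Baseline to allow for laboratory delays.

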8.4. Randomization Criteria

Only those patients meeting all of the following randomization criteria are eligible for randomization:

1. Continues to meet all inclusion and exclusion criteria, including urine and blood test results and is successfully and consistently utilizing the diary system.
2. Patient's FM pain satisfies the following criteria, as assessed by diary pain scores (24 hour recall):
 - a. A mean pain intensity score ≥ 4 and ≤ 9 on the 11-point (0-10) NRS scale for the 7 days immediately preceding Visit 2, and

- b. No more than 2 individual days with a score <4 on the 7 days immediately preceding Visit 2, and
- c. No score of 10 on any of the 7 days immediately preceding Visit 2, and
- d. Pain scores recorded on at least 5 out of the 7 days immediately preceding Visit 2.

If the patient does not satisfy these randomization criteria, the patient has failed to qualify for this study and should be considered a screen failure, with the reason documented. With Medical Monitor approval, if the patient is otherwise considered a qualified and compliant patient, Visit 2 may be delayed for up to 7 days to accommodate situations in which the patient has been unable to record 5 of 7 days of pain scores due to acceptable extenuating circumstances. There is no requirement for a Follow-Up visit for screen failures.

8.5. Patient Withdrawal Criteria

In accordance with the Declaration of Helsinki, human subjects have the right to withdraw from the study at any time for any reason. The Investigator and Tonix also have the right to remove patients from the study. Additional information regarding withdrawal or discontinuation of patients is described in detail in [Section 11.5.2](#).

9. TREATMENT OF PATIENTS

9.1. Prior and Concomitant Medications

Patients who are taking certain medications to manage their FM are eligible for the study if they are willing and able (and it is medically reasonable for them) to be withdrawn from those medications that are specifically excluded by the protocol and they agree to refrain from further usage during this study. The specific medications that must be withdrawn include milnacipran, pregabalin, duloxetine, tramadol, gabapentin, any form of cyclobenzaprine (AMRIX[®], FEXMID[®] or generic cyclobenzaprine), tapentadol, amitriptyline and other tricyclic antidepressants, trazodone, narcotics/opioids and naltrexone (including CONTRAVE[®]). In addition, certain other medications are prohibited and may require washout, or exclusion of patients for whom washout is not appropriate (e.g., benzodiazepines, anticonvulsants (except when used as migraine prophylaxis), levomilnacipran, mirtazapine, nefazodone, St. John's wort, phentermine, diethylpropion, muscle relaxants (e.g., methocarbamol, baclofen, carisoprodol), and systemic use of strong CYP3A4 inhibitors as defined in [Appendix 1](#) (i.e., topical use is not excluded).

All patients undergoing washout must complete a 3-week drug-free interval prior to the Baseline/Randomization visit (Visit 2); this will provide two weeks of washout prior to the 7 days leading up to Visit 2 when baseline efficacy data will be collected on the daily diary. Any patient with a positive screening UDS who is washing off an opioid, amphetamine, or benzodiazepine must return to the clinic for a repeat UDS before they begin their 7-day baseline data collection period leading up to Visit 2.

In general, patients utilizing benzodiazepines on a chronic or regular basis should not be considered for the study; however, washout may be considered for those patients utilizing them only on an occasional or as-needed basis (e.g, three times per week or less, on average). In addition, patients taking benzodiazepines for restless leg syndrome should not be considered, since washout would not be advised. Buspirone, however, is allowed.

Several benzodiazepines are not easily detected by the in-clinic urine dipstick; therefore, patients positive for benzodiazepines at Screening and deemed appropriate for washout will require a centrally-interpreted repeat UDS conducted prior to the beginning of the 7-day baseline data collection period prior to V2. All other repeat urine drug screens can be conducted on-site. All repeat UDS results must be confirmed negative before the patient can be randomized.

Patients using non-benzodiazepine hypnotics (e.g., zolpidem, eszopiclone, zaleplon) on a chronic, nightly basis should not be enrolled; however, patients utilizing these medications on an infrequent or occasional basis only (e.g., three times per week or less, on average) may be considered. Similar to the benzodiazepines, drugs in this class of medication can negatively impact sleep architecture; therefore, patients utilizing either non-benzodiazepines or benzodiazepines should be discussed with the Medical Monitor early during the screening process to determine their suitability for the study and to determine whether washout is clinically advisable. Patients washing off non-benzodiazepines should not be randomized if they are unable to discontinue their use and remain drug-free through their 7-day baseline data collection period leading up to Visit 2. The patient's ability to successfully discontinue their use of

excluded sleep therapies should be carefully assessed, since UDS testing is not available for non-benzodiazepine hypnotics.

After randomization, sedating antihistamines (e.g., diphenhydramine, hydroxyzine) may be used as needed for insomnia; however, patients will need to refrain from their use during the week of baseline data collection leading up to Visit 2. Patients should track their use of sedating antihistamines in between study visits so that changes in usage during the course of the study can be tracked and recorded.

The use of melatonin, ramelteon, and valerian root is not restricted. Similarly, the use of cannabidiol (CBD) products is not restricted, but like all other allowed concomitant medications, its usage should have been stable for at least 30 days prior to randomization, and usage should remain stable during the study. Additionally, the use of CBD products should not be started after randomization. All CBD products should be added to the concomitant medication source and case report form (CRF).

Due to the exclusion of all opioids during the Treatment Phase of the study, patients requiring opioids on a regular or frequent basis for any indication should not be considered. In addition, patients with neuropathic pain in addition to fibromyalgia should not be washed off of gabapentin, pregabalin or any other anticonvulsant, and therefore should not be considered for the study.

At Screening Visit 1 and after signing the written informed consent, any required washout should be discussed with the patient and plans made for an appropriate schedule for reducing/stopping any excluded medications. This down titration and withdrawal must be accomplished so that the patient is medication free for at least 21 days prior to randomization. This will provide 14 days off the excluded medication before the patient starts the 7-day run-in phase during which critical baseline efficacy data are collected by means of the daily diary. Any additional time required for down-titration would be in addition to this 21-day washout requirement. For this reason, patients can remain in screening for up to 35 days, which provides an additional 2 weeks for down-titration, if required. For extenuating circumstances, the duration of the Screening period may be increased to up to 49 days with Medical Monitor approval.

Other chronic prescription or over-the-counter medication not specifically excluded by an exclusion criterion may be continued in the study, provided that the patient has been on this medication for at least 30 days at a stable dose (except for allowed antidepressants, which require 90 days at stable dose) from the date of randomization, and usage is expected to remain stable throughout the study. Allowed medications include, but are not limited to, hormonal therapy (contraceptives and replacement therapy), anti-hypertensive agents, lipid-lowering medications, selective serotonin reuptake inhibitors (SSRI) and other allowed antidepressants (e.g., venlafaxine, desvenlafaxine, bupropion, vilazodone).

Acetaminophen (up to 3000 mg/day) and non-steroidal anti-inflammatory drugs (NSAIDs) may be continued in a stable fashion for osteoarthritis or other allowed indications (e.g., aspirin for cardioprophylaxis), or used as needed for other sources of acute, minor pain. Note that acetaminophen and NSAIDs may be taken either on a regular basis, or on an as-needed (prn) basis; however, if used as-needed, the Investigator should ascertain the patient's typical pattern of usage (e.g., average dosage and frequency per defined time interval) so that this information can be recorded on the CRF. Any significant change in the patient's usage of any medication,

including those taken only as needed, should result in an update to the CRF. The CRF entry for any prn medication is expected to include an estimation of the patient's average dosage and frequency per defined time interval.

Patients on allowed antidepressants due to a history of depression should only be considered for the study if no changes in antidepressant agent or dose have occurred during the 90 days leading up to randomization, and no changes are anticipated or planned during the treatment phase of the study. In addition, FM patients with comorbid depression who are being treated with duloxetine, milnacipran, levomilnacipran, monoamine oxidase inhibitors, or tricyclic antidepressants should in general not be considered for the study since washout of these agents could destabilize their psychiatric status.

NOTE: Participating patients receiving treatment with antidepressants should be cautioned about the possibility of serotonin syndrome, which has been reported in patients receiving cyclobenzaprine with SSRIs, serotonin-norepinephrine reuptake inhibitors (SNRI) and related agents. This will be included in the ICF.

New medications that are deemed required, in the opinion of the Principal Investigator or another physician, will be allowed, including medications needed to treat adverse events. After randomization, if there is a requirement for treatment with an acute opioid or other treatment that may confound the evaluation of pain at critical times during the study (defined as the week prior to Visits 3, 4, 5 or 6), the Investigator may consult with the Medical Monitor to potentially delay the study visit until the medication is no longer needed. At a minimum, no opioid/narcotic should have been utilized within 2 days of a study visit, and ideally there will have been no usage during the 7 days prior to these visits. While it is understood that opioid usage will occasionally be necessary and unavoidable, it could have consequences on the patient's data.

Similarly, if there is a requirement for acute, short-term opioid usage during the screening phase, the start of the 7-day run-in phase should be delayed to ensure at least 2 days between the last opioid dose and the beginning of the 7-day run-in phase. In other words, there may be some circumstances when the unexpected requirement for short-term opioid usage, specifically due to an *acute* medical, dental or surgical condition, does not require the full 21-day washout. This provision only applies to *acute* pain conditions – not to opioid usage due to a flare in patient's FM or other chronic pain condition. Any requirement for acute opioid usage during the screening phase should be brought to the attention of the Medical Monitor to ensure adequate washout prior to randomization.

Patients should refrain from drinking grapefruit juice or eating grapefruit during the study due to its ability to inhibit CYP3A4 activity. Aside from this restriction, there are no other food or fluid restrictions in this study except for the instructions pertaining to dosing ([Section 10.2](#)).

Patients using teeth-whitening products such as whitening strips or prescription whitening products must agree to discontinue their use from the day of randomization until the end of their study participation.

Any concomitant medications or other treatments must be recorded in the patient's medical record and case report form along with the dose and dates of treatment.

